This will be a longitudinal study in which patients will be examined with a cluster of visits biannually. We will recruit patients with:

1. Glaucoma;
2. Suspicion of having glaucoma;
3. Non-glaucomatous optic neuropathies;
4. Age-related macular degeneration (AMD);
5. Retinal degenerations;
6. Other diseases involving the visual pathways such as optic neuritis, tumors or ischemic neuropathy.

Patients with eye diseases or suspected of having eye diseases will be recruited from [name] clinic by verbal communication. Staff members at the Duke Eye Center will also be invited to recommend potential participants for the study, in conformance with the Duke Human Subjects Committee Guidelines. Healthy participants will be recruited from patient's spouses or relatives for comparison and to establish normative levels, and will also be recommended from eye doctors from the comprehensive clinic who treat this population.

General evaluation:

As part of the study all participants will undergo the following general exams:

1. Review of medical history;
2. Blood pressure and heart rate;
3. Height and weight;

Ophthalmological evaluation:

As part of the study all participants will undergo a comprehensive ophthalmologic examination including:

1. Low contrast sensitivity testing;
2. Best-corrected visual acuity;
3. Slit lamp biomicroscopy;
4. Serial measurement of the intraocular pressure measurement before and after drinking water;
5. Gonioscopy;
6. Corneal thickness measurement (pachymetry);
7. Corneal hysteresis measurement (Ocular Response Analyzer, Reichert, Inc.);
8. Ocular axial length;
9. Corneal curvature;
10. Anterior chamber measurement;
11. Dilated funduscopy examination;
12. Stereoscopic optic disc photography;
13. Measurement of amount of lens opacity (cataract) by the HD Analyzer system (Visiometrics, Inc.);
14. Automated perimetry with the 24-2 and 10-2 Swedish Interactive Threshold Algorithm (SITA; Carl Zeiss Meditec, Inc.) and fundus perimetry with Compass (CenterVue, Inc.);
15. Spectral domain optical coherence tomography (SDOCT);
16. Swept-source optical coherence tomography (SSOCT);
17. Optical coherence tomography angiography (OCTA);
18. Macular pigment optical density (MPOD).
19. Diopsys NOVA (Diopsys, Inc.) visual evoked potentials (VEP) and electroretinogram (ERG).

The following tests are considered research related:

Questionnaires:

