3. Be able and willing to provide signed informed consent and follow study instructions

Exclusion criteria:

1. Subjects will be excluded if they present with any systemic or ocular conditions that in the opinion of the Principal Investigator may prevent them from completing the tests (e.g. history of seizures or pathologies affecting the vestibular system or lower limbs).
2. Women of child-bearing potential will be excluded from tests that require pupil dilation, unless they have already received dilating drops as part of their standard of care. Pregnant women may self-report pregnancy testing and not undergo formal pregnancy testing since the SOC in ophthalmology is to not test for pregnancy or dilate the eyes of women who are of childbearing age.

Glaucoma Arm

To be considered glaucomatous, patients will be required to have at least two consecutive and reliable standard automated perimetry (SAP) examinations with either a pattern standard deviation (PSD) outside the 95% normal limits or a glaucoma hemifield test (GHT) result outside the 99% normal limits. Patients considered suspects for glaucoma must have an IOP greater than 21mmHg or suspicious appearance of the optic nerve head but with reliable normal visual fields, defined as a PSD within 95% confidence limits and a GHT result within normal limits. To be considered healthy, subjects have to have IOP<22mmHg with no history of elevated IOP and with at least two reliable normal visual fields, defined as a PSD within 95% confidence limits and a GHT result within normal limits.

Age-related macular degeneration (AMD) Arm

Patients will be considered as having AMD if one or more of the following are present on posterior biomicroscopy (fundoscopy), indirect ophthalmoscopy or Optical Coherence Tomography (OCT) exams:

1. Presence of at least intermediate-size drusen (63µm or larger in diameter)
2. Retinal pigment epithelium (RPE) abnormalities such as hypopigmentation or hyperpigmentation
3. Reticular pseudodrusen (also called sub retinal drusenoid deposit)

4. Presence of any of the following features: geographic atrophy of the RPE, choroidal neovascularization (exudative, wet), polypoidal choroidal vasculopathy, or retinal angiomatous proliferation.

Other pathologies Arm

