Subjects will be referred from the Duke Eye Center care providers after a comprehensive clinical eye examination from a routine visit. If the last clinical eye examination is not within 6 months of the study visit, the participant will be examined by the PI, with no additional cost to the patient. Participants will also undergo other tests that will allow a better understanding of the relationship between potential visual impairment caused by their diseases and the ability to perform daily tasks. The results of the study are likely to provide important information on how eye diseases are associated with visual impairment, task performance and quality of life. This may lead to development of better tests to predict patient performance and visual loss, which could benefit patients with these diseases.

COSTS TO THE SUBJECT

All procedures described here, including both visits, will be free of charge to patients. There is no additional cost for the subject if they participate in the study. Study related activities/procedures will be paid by the study.

DATA ANALYSIS & STATISTICAL CONSIDERATIONS

Describe endpoints and power calculations. Provide a detailed description of how study data will be analyzed, including statistical methods used, and how ineligible subjects will be handled and which subjects will be included for analysis. Include planned sample size justification. Provide estimated time to target accrual and accrual rate. Describe interim analysis including plans to stop accrual during monitoring. Phase I studies, include dose escalation schema and criteria for dose escalation with definition of MTD and DLT.

For all test results and variables, an extensive data preparation will be performed, with analysis of distributions, error checking and cross-tabulation. We will investigate differences in the results of the tests between diseased and healthy participants. Normality of variables will be assessed using histograms and Shapiro-Wilk tests. Student t tests will be used for comparison of means of normally distributed variables, whereas Mann-Whitney tests will be used for non-normally distributed variables. Generalized estimating equations (GEE) will be used to take into account potential correlations between tests results from the two eyes of the same subject.

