Mixed models will be used for analysis of longitudinal data collected over time. These methods can successfully take into account longitudinal correlations among observations as well as correlations of results of eyes nested within patients. We will also use methods such as survival analysis (Weibull and Cox models) to assess prediction and joint longitudinal survival models.

All statistical analyses will be performed by [name] and associates using commercially available statistical and mathematics software Stata (version 15; StataCorp LP, College Station, TX, USA), MATLAB (Mathworks, Inc.), and MPLUS (Muthen & Muthen). Additional analysis and image processing from de-identified data will be performed by GA Tech's PI [name], and [name] and associates. An alpha level will be generally set at 0.05, unless there is a need to correct for multiple comparison testing which will then be performed by procedures such as false discovery rate.

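### Person-level comparisons of diseased and healthy participants make no allowance for unequal variances, so Student's t test can miss its 5% level if the arms differ in both size and spread

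*Combined protocol and SAP*

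**What the plan says.** Under Data Analysis & Statistical Considerations, the comparison is stated as: "We will investigate differences in the results of the tests between diseased and healthy participants". The method follows: "Normality of variables will be assessed using histograms and Shapiro-Wilk tests", and then "Student t tests will be used for comparison of means of normally distributed variables, whereas Mann-Whitney tests will be used for non-normally distributed variables". No Shapiro-Wilk threshold is given, nor whether normality is judged per arm, on pooled data or on residuals. No variance check or unequal-variance test is mentioned. The significance level is given as "An alpha level will be generally set at 0.05, unless there is a need to correct for multiple comparison testing", with false discovery rate named as a possible correction.

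The same section plans GEE for results from two eyes of one person and mixed models for longitudinal data. Neither is tied to the normality check.

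No sample size, arm size, allocation ratio or SD appears. The template prompt "Include planned sample size justification" is left unanswered.

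On spread, Selection of Subjects says: "To be considered healthy, subjects have to have IOP<22mmHg with no history of elevated IOP", together with at least two reliable normal fields. The glaucoma definition asks for repeated abnormal fields, "with either a pattern standard deviation (PSD) outside the 95% normal limits" or an abnormal hemifield test, with no ceiling on severity. The AMD definition runs from intermediate drusen to geographic atrophy and neovascular disease. On numbers, Design & Procedures says only: "Healthy participants will be recruited from patient's spouses or relatives for comparison and to establish normative levels", plus referrals from the comprehensive clinic. It sets no quota or matching ratio.

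**The concern.** Student's t test, in its usual meaning, estimates one common variance from both arms. If the smaller arm is the more variable, the pooled standard error is too small and false positives rise. If the larger arm is the more variable, the standard error is too large and power is lost. The plan's only safeguard is a check of shape, which does not look at variance.

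The controls are truncated by their entry criteria and the disease groups are open-ended, so unequal spread is plausible, at least for visual-field measures and outcomes that follow them. Six diagnostic groups of unstated size are to be compared with one control group. The same test could therefore be too liberal for a small disease arm and too strict for a large one. A false discovery rate procedure cannot repair this, because it takes the p-values as valid.

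The outcomes exposed are those with one value per person: questionnaires, driving simulator, virtual reality tasks and balance. They bear directly on the study's purpose.

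**Working it through.** The plan has no figure to reproduce, so the check asks how far the stated rule departs from 5% under a range of assumptions.

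**Inputs.** Alpha 0.05 is from the plan; two-sided is assumed. Arm sizes and the SD ratio (diseased over healthy) are assumptions. Data are normal with equal true means. The rule is read as Shapiro-Wilk at 0.05 in each arm, then pooled t if both pass and Mann-Whitney otherwise; the cut-off and per-arm testing are also assumptions.

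**Formula for the pooled t test (large-sample).** With diseased n1 and SD s1, and healthy n2 and SD s2:

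- true variance of the difference: V = s1²/n1 + s2²/n2
- variance the test uses: E = sp² × (1/n1 + 1/n2), where sp² = [(n1−1)s1² + (n2−1)s2²]/(n1+n2−2)
- r² = V/E, and type I error ≈ 2 × [1 − Φ(1.96/r)]

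**Worked case: 30 diseased, 150 controls, SD ratio 2.** V = 4/30 + 1/150 = 0.1400. sp² = (29×4 + 149×1)/178 = 1.489. E = 1.489 × 0.04 = 0.0596. r² = 2.351, r = 1.533, 1.96/r = 1.278, and type I error ≈ 20.1%.

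**Worked case: 150 diseased, 50 controls, SD ratio 2.** V = 4/150 + 1/50 = 0.0467. sp² = (149×4 + 49×1)/198 = 3.258. E = 3.258 × 0.02667 = 0.0869. r² = 0.537, r = 0.733, 1.96/r = 2.674, and type I error ≈ 0.7%.

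**Simulation against formula** (ranges cover repeated runs; at 6,000 datasets the Monte Carlo standard error near 5% is about 0.3 percentage points):

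| Diseased : healthy | SD ratio | Formula, pooled t | Pooled t, no normality check | Stated rule |
|---|---|---|---|---|
| 30 : 150 | 1.5 | 13.2% | 13.2-13.7% | 12.6-13.6% |
| 30 : 150 | 2 | 20.1% | 19.7-20.5% | 19.2-20.2% |
| 50 : 150 | 1.5 | 10.7% | 11.1% | 11.3% |
| 50 : 150 | 2 | 15.1% | 14.8% | 14.5% |
| 150 : 50 | 1.5 | 1.7% | 1.7-1.9% | 1.9-2.2% |
| 150 : 50 | 2 | 0.7% | 0.7-0.9% | 0.9-1.1% |
| 100 : 100 | 1.5 | 5.0% | 5.0% | 5.0-5.4% |
| 100 : 100 | 2 | 5.0% | 4.5% | 4.7-4.9% |

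Welch's test stayed between 4.3% and 5.5% in every setting, including skewed ones. At the milder SD ratio of 1.25, the stated rule gave 8.7% for 30 : 150 and 3.3% for 150 : 50.

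**What causes the error.** The last two columns are almost the same, so the normality check contributes almost nothing. With equal SDs and the same shape in both arms, the rule held 4.6-5.2%. With normal data, both arms passed Shapiro-Wilk in 89.8-90.7% of datasets at SD ratios of 1, 1.5 and 2 alike, close to 0.95² = 90.25%. The check does not see the variance.

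**Power.** With 150 diseased and 50 healthy, and a difference set for about 80% Welch power, Welch reached 0.79 and the stated rule 0.66 at SD ratio 1.5. At SD ratio 2 the figures were 0.80 and 0.56.

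**Skewed data.** With gamma data (shape 4) in both arms, the rule almost always chose Mann-Whitney. At 100 : 100 it rejected in 11.0% and 19.4% of datasets with equal means, at SD ratios of 1.5 and 2.

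**The case against.** Five points are made on the other side.

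- **Arms may not differ.** A reader might infer that arm sizes and spreads will differ here. The documents do not support that: they give no sizes, ratio or SDs, and recruiting spouses or relatives does not show imbalance in either direction. This objection stands, so the concern is conditional. Unequal spread is plausible from the entry rules, and equal sizes are not secured.
- **The pre-test is not to blame.** A reader might also infer that choosing the test by Shapiro-Wilk is what breaks the error rate. The calculation shows otherwise. Removing the check while keeping Student's t would leave the errors as they are.
- **Severity mixing also shifts the mean.** If spread rises because an arm mixes mild and severe patients, the null is false. With an assumed 40% severe patients, SD ratios of 1.5 and 2 imply mean shifts of 0.92 and 1.4 control SDs, and both the stated rule and Welch rejected in 88-100% of runs. This limits how literally the type I figures apply, and the documents name no outcome with unequal spread and equal means. It does not rescue the standard error whenever pooled t is used. From r above, the pooled standard error is 1/1.533 = 0.65 of the true one for 30 : 150, and 1/0.733 = 1.36 of it for 150 : 50, at SD ratio 2 and whatever the means.
- **Scope.** GEE and mixed models are planned separately, so it would be wrong to read this as affecting every p-value in the study. This stands. The plan also mentions histograms, so the choice need not be mechanical, but a histogram does not make the pooled test valid.
- **Mann-Whitney is not a test of means.** Its rejections under skewness are errors only if a mean difference is the target. This stands; the skewed results show only that Mann-Whitney cannot stand in for a comparison of means.

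**Conclusion.** The point holds in a conditional form. For cross-sectional outcomes with one value per person, the plan's comparison of means has no protection against unequal variances, and its normality check supplies none. If arms differ in both size and spread, type I error at a nominal 5% moves to roughly 13-20% for a small, more variable disease arm (30 against 150 controls) and to roughly 1-2% for a large one (150 against 50 controls), with the power loss shown above in the second case. These figures rest on normal data, equal means, a two-sided test, the pooled reading of Student's t, and assumed sizes and SD ratios of 1.5 to 2. With equal arms and normal data the error disappears. The plan does not say whether disease groups are compared with controls one by one or together, so the direction cannot be settled from the documents.

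The study names no primary endpoint, so no single conclusion hangs on this. It is still a definite and cheap improvement in method.

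**What to change.** For outcomes with one value per person, replace Student's t with Welch's t test, or a regression with robust standard errors where covariates are wanted. Set it in advance as the comparison of means for every such outcome, not conditional on Shapiro-Wilk. State that the target is a difference in means. Report Mann-Whitney as a sensitivity analysis for skewed outcomes. Leave the GEE and mixed-model plans as they are.

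A blanket rule to log-transform times and path lengths is not advised. The virtual reality probe outcomes, which measure time and path near the target, can be zero, and hidden-target searches are limited to 2 minutes, which a log does not address.

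The cost is a few sentences in the analysis section. The statistical price is a very small loss of power when variances are in fact equal. A check with equal SDs and a difference of 2.80 × √(1/n1 + 1/n2), using 20,000 datasets per setting, gave Welch 77.5% against 79.0% for pooled t at 30 : 150, 79.1% against 80.0% at 150 : 50, and 79.9% for both at 100 : 100.

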Participants will be tested on a driving simulator. The simulator system consists of a panel of screens, a wheel drive, and a foot pedal, similar to a real car, all connected into a computer. Participants are asked to perform simple tasks such as follow a vehicle, keep up with the speed limit and avoid obstacles. Data collection includes several variables such as speed, lane deviation, time of reaction, vehicle control and obstacle avoidance. If a patient feels dizzy the exam can be interrupted at any time. The duration of testing with the simulator is about 15 minutes. As this is an experimental procedure, no results will be reported to the DMV with regard to driving ability.

Virtual Reality Tests:

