Virtual reality tests will be conducted using virtual reality goggles (HTC Vive, Samsung Gear VR or FOVE). The tasks include scenarios replicating daily activities such as driving through a road, walking through a virtual environment or searching for objects. In order to navigate through the environment, subjects will use a steering wheel or joystick. The estimated duration of the test is 30 minutes. In the task of navigation, the subject will find him or herself near a wall in a rectangular room with colored walls, different objects on each wall, and different objects (couch, table statue, etc.) at various locations. The subject will be asked to move to and step upon a green tile that is displayed at some random location in the room. Once the target location is attained, the display is turned off for a short period. The task will then begin again, but with a different starting position. These initial tests are designed to assess the subject's ability to move from one location to another in a virtual environment. Subjects that can achieve sufficient proficiency in the target-visible protocols will then be instructed that the next series of tests will require them to find a hidden target tile and that they will be asked to remember its location. In these protocols, the subjects will be given a limited amount of time (2 minutes) to locate the target, which will become visible when it is reached, and their path and time to target discovery recorded. Path length and path topology will be measured in real time. The test will be repeated, from the same starting location, at least 5 times or until no improvement in time/distance to target is observed by the experimenter, who is analyzing the test outcomes on a tablet in real time. After a 5-minute rest period with no visual stimulus, the subject will be asked to repeat the task for a "probe" trial. This time the search will be limited to 30 seconds or to the shortest time attained in the prior trials, without the target becoming visible. The outcome measurement will be time spent and path length in the vicinity of the target, as a measure of spatial memory and spatial navigation strategy. Depending on the data obtained in this set of trials, the subject will be asked to continue with further tests of increasing difficulty,

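### For person-level outcomes measured at a single visit, the diseased-versus-healthy comparison is assigned tests that cannot adjust for age, and no age adjustment or matching is planned

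*Combined protocol and SAP*

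**What the plan says.** In the Combined protocol and SAP, Data Analysis & Statistical Considerations opens with data preparation: "For all test results and variables, an extensive data preparation will be performed, with analysis of distributions, error checking and cross-tabulation". It then states the comparison, "We will investigate differences in the results of the tests between diseased and healthy participants", and the methods, "Student t tests will be used for comparison of means of normally distributed variables, whereas Mann-Whitney tests will be used for non-normally distributed variables".

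The other methods have other stated jobs. GEE is given for eye-level results: "Generalized estimating equations (GEE) will be used to take into account potential correlations between tests results from the two eyes of the same subject". The role of the next method concerns repeated measurement: "Mixed models will be used for analysis of longitudinal data collected over time". Survival and joint models are listed for prediction.

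The design sections bear on the comparison as follows:

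- Design & Procedures: healthy participants are patients' spouses or relatives, or are suggested by doctors in the comprehensive clinic.
- Selection of Subjects: one age range, 40 to 90 years, applies to everyone.
- Glaucoma Arm: a healthy subject is defined by intraocular pressure, its history and visual fields. Age is not part of the definition.
- Scheduled Visits, amendment 1.21: normal subjects do the test battery once and are not followed up.

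Many outcomes describe a person, not an eye. For the driving simulator, for example: "Data collection includes several variables such as speed, lane deviation, time of reaction, vehicle control and obstacle avoidance".

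**The concern.** The groups are formed by diagnosis, not by randomisation, so nothing in the design balances age between them. One arm is defined by an age-related disease. Speed, reaction time, balance and navigation may well change with age; the documents give no figures on this.

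If the diseased group is older and performance worsens with age, an unadjusted comparison overstates the effect of disease. If the diseased group is younger, it understates or hides that effect. A larger sample does not help: the bias stays the same while the standard error shrinks, so a spurious difference becomes more likely to reach significance. The comparison with healthy participants is also meant to supply normative levels, so an age imbalance could carry over into those.

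**Working it through.** **Step 1. Is an adjusted method assigned to this comparison?** The plan states no sample size, effect size or power, so there is no figure to reproduce. The check is to set each stated method against single-visit, person-level data.

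| Method | Stated purpose | Reaches this comparison? |
|---|---|---|
| Student t / Mann-Whitney | Group comparison, chosen by normality | Yes; takes no covariate |
| GEE | Correlation between a subject's eyes | No; the outcome belongs to the person |
| Mixed models | Longitudinal data | No, where there is one visit |
| Survival and joint models | Prediction | No |

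No covariate is named for any of these models. No matching or stratification appears in the recruitment, eligibility or analysis sections.

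**Step 2. What would an age gap do? (illustration)** From the document: alpha 0.05; its sidedness is not stated, and two-sided is assumed. Assumed, and not in the documents: within-group age SD 11 years, age-outcome correlation r of 0.2, 0.3 or 0.5, 100 per group, no disease effect, linear age effect.

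- Spurious standardised difference: d = r × gap / 11.
- Noncentrality: d × √(n/2), with √(100/2) = 7.071.
- Rejection probability: noncentral t with 2n − 2 = 198 degrees of freedom.

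Example, 5-year gap and r = 0.3: d = 0.3 × 5 / 11 = 0.136; noncentrality = 0.136 × 7.071 = 0.964; rejection probability 0.160.

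| Age gap | r = 0.2 | r = 0.3 | r = 0.5 |
|---|---|---|---|
| 0 years | 5.0% | 5.0% | 5.0% |
| 2 years | 5.8% | 6.7% | 9.8% |
| 5 years | 9.8% | 16.0% | 35.9% |
| 10 years | 24.9% | 48.4% | 89.2% |

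At a 5-year gap the range over r is 7-20% with 50 per group and 15-62% with 200 per group.

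**Step 3. Simulation check.** 20,000 null data sets per setting, 5-year gap, 100 per group, r = 0.2, 0.3, 0.5:

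- Student t: 9.8%, 16.0%, 36.0%.
- Mann-Whitney: 9.5%, 15.3%, 34.6%.
- Linear regression on group and age, robust standard errors: 4.9%, 4.7%, 4.7%.

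A separate simulation (4,000 data sets, age SD 10, r = 0.3, 100 per group) gave, for Student t, Mann-Whitney and age-adjusted linear regression, 17.6%, 17.2% and 5.0% at a 5-year gap, and 5.0%, 4.7% and 4.8% with no gap. The adjusted model keeps its level here because the data were generated with a linear age effect and a common slope.

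**Step 4. Cost in precision.** In the Step 3 set-up, the ratio of adjusted to unadjusted standard error was 0.90-1.02 at a 5-year gap, 0.96-1.09 at 10 years and 1.19-1.34 at 20 years.

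**The case against.** **Mixed models are already planned and can carry age.** This stands in part. Before amendment 1.21 the schedule of six-monthly visits made no exception for controls, so some may have repeat data, and the mixed-model sentence is not restricted to patients or to eyes. A reader might infer that the t and Mann-Whitney tests are the only method for every person-level outcome. The documents do not support that; the point holds for single-visit data. Where mixed models or GEE do apply, the gap is that no age term is named.

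**The groups may be similar in age.** This is possible. Recruiting spouses may narrow a gap, although relatives may be of another generation and neither source is a matching rule.

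**The comparison is one part of the study.** The stated purpose also covers the relation of task performance to clinical measures and to patterns of visual damage, and the plan does not say that conclusions rest on these tests alone. This is a fair limit on the weight of the point.

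**Related factors are collected.** The questionnaires cover cognition, depression, physical activity and socioeconomic status, and the planned software can fit adjusted models. Collecting a factor is not a plan to adjust for it. Likewise, cross-tabulation could reveal an age gap but would not remove it.

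**Multiplicity control is foreseen.** The 0.05 level applies "unless there is a need to correct for multiple comparison testing which will then be performed by procedures such as false discovery rate". That addresses the number of tests; it does not remove confounding.

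**Conclusion.** The point holds in a limited form. For person-level outcomes measured at a single visit, the stated tests cannot adjust for age, and the plan names neither adjustment nor matching. An age gap combined with an age-dependent outcome would be attributed to disease.

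A reader might go further and infer that the results will be biased. The documents do not show that: they give no ages by group, so the presence, size and direction of any bias are unknown. Confidence is high in the omission and does not extend to its consequence. The false-positive rates (5% with no gap, 10-36% at 5 years, 25-89% at 10 years) show what could happen under the assumed age SD, correlations and group size, and are not estimates for this study.

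This is a cheap improvement. It replaces a stated test with a more suitable one, and so goes beyond asking for more detail.

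**What to change.** In Data Analysis & Statistical Considerations, replace the sentence on t and Mann-Whitney tests with wording such as: *The main diseased-versus-healthy analysis of each outcome will be a regression on group and age, using a model suited to the type of outcome. Age and its overlap will be reported by group. Where GEE or mixed models are used for this contrast, age will be included. Unadjusted Student t and Mann-Whitney results will be descriptive.*

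No new data are needed, since age is already required for eligibility and suitable software is planned. The costs are:

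- slightly more analysis work;
- some loss of precision if the age gap is large (under the assumed inputs, a standard error up to about 9% larger at 10 years and 34% at 20 years);
- reliance on a correctly modelled age effect;
- extrapolation where the groups' ages do not overlap, which is why overlap should be reported.
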